9.2.2 Stopping Rules for Toxicity

A stopping rule for safety will be applied separately to each arm for the Phase 2 study. Six patients on each arm from the safety lead-in study are included in the phase II study and will have already been evaluated for safety. Within each arm, we will stop accrual if there are 3 SigAEs among the next 10 randomized patients (total accrual per arm would be 16 patients). Following these 10 patients, safety would then be assessed cumulatively and accrual will continue unless 20% or more of all treated patients on a single arm experience a SigAE as defined in section 7.3.2. If this frequency of SigAEs is observed in one arm but not in the other, then the arm with the SigAEs will be discontinued while the arm without sigAEs will continue.

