3.1 Safety Analysis

Because SipT treatment is associated with minimal toxicity, and an active dose of ipilimumab has been established (no MTD has been defined) with tolerable side effects, we propose to perform a safety analysis with standard SipT treatment and the 3 mg/kg dose of ipilimumab. Twelve patients will be randomized to either of the 2 scheduling arms (immediate vs. delayed) (6 per arm). After randomizing the initial 6 patients to each arm, the frequency and grade of AEs will be evaluated.

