9 STATISTICAL METHODOLOGY

9.1 Sample Size Considerations

9.1.1 Safety Lead-in

Six patients at the 3 mg/kg dose of ipilimumab will be randomized to Arm 1 and 2, immediate versus delayed ipilimumab after 4 doses of SipT. If DLTs are encountered as defined above (Section 3.1), then one or both arms may be discontinued. 6 patients will be required to complete this phase of the study.

9.1.2 Phase 2

Primary Immune Objective: This is a multicenter non-comparative randomized Phase 2 trial with the primary objective of immunologic efficacy in addition to safety. Immune response is defined as an IgG antibody response to either PAP or PA2024 by study week 20. The IgG antibody response will be determined with an ELISA assay with a positive response defined as titer > 1:400. To achieve a 40% immune response rate indicating immune activity versus a null hypothesis of 15% indicating lack of immune activity assuming a 2-sided type I error of 5% and 81% power will require 27 total patients per arm. This is based upon the exact binomial test for a single sample. The null hypothesis of 15% is based off an observed anti-PAP IgG response rate of 17.7% seen at a similar time interval in patients treated with sipuleucel-T in the three phase 3 clinical trials⁴⁶. Therefore, an additional 21 patients beyond the safety lead-in phase will be accrued to each arm (an additional 42 patients). The total number of evaluable patients for the Phase 2 study will be 54 patients with accrual up to 66 patients possible. Patients will be accrued at UCSF and MDACC with the randomization to ipilimumab timing stratified by institution.

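### With two or more lead-in SigAEs in an arm, accrual can go on after the plan's own 20% rule is already certain to stop that arm

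*Combined protocol and SAP*

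**What the plan says.** Section 9.2.2 (Stopping Rules for Toxicity) works arm by arm. The six lead-in patients per arm "are included in the phase II study and will have already been evaluated for safety". The first rule covers the ten patients after them: "we will stop accrual if there are 3 SigAEs among the next 10 randomized patients (total accrual per arm would be 16 patients". The second starts once those ten are in: "accrual will continue unless 20% or more of all treated patients on a single arm experience a SigAE".

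For the lead-in itself, Section 3.1 says "Twelve patients will be randomized to either of the 2 scheduling arms (immediate vs. delayed) (6 per arm", and "After randomizing the initial 6 patients to each arm, the frequency and grade of AEs will be evaluated". Section 9.1.1 adds "If DLTs are encountered as defined above (Section 3.1), then one or both arms may be discontinued", and gives the size as "6 patients will be required to complete this phase of the study". Section 9.1.2 then says "Therefore, an additional 21 patients beyond the safety lead-in phase will be accrued to each arm (an additional 42 patients".

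**The concern.** The lead-in patients are in the denominator and numerator of the cumulative rule but are left out of the 3-in-10 trigger. A SigAE, once it has happened, cannot be undone. So the cumulative result at 16 patients can be settled well before patient 16, and in an arm with several lead-in SigAEs it can be settled before the 3-in-10 trigger is met. Further patients would then be randomized and treated in an arm that the plan's own threshold has already closed.

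Three defects in the surrounding text make the rule harder to apply:

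- The lead-in rule refers to DLTs defined in 3.1, which defines none, so the lead-in has no usable numeric criterion.
- The first stage counts events and the second counts patients. Read literally, three events in one patient meet the first trigger.
- Section 9.1.1 puts the lead-in at 6 patients and 3.1 at 12.

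**Working it through.** **Inputs.** 6 lead-in patients per arm (3.1, 9.2.2); 10 more under the first rule, trigger 3 (9.2.2); cumulative threshold 20% of treated patients (9.2.2); 21 further patients per arm after the lead-in (9.1.2). The SigAE risk is not given, so p is an assumption.

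**The plan's own figures.** 6 + 10 = 16 per arm reproduces the stated accrual, and 6 + 21 = 27 the arm size. For the lead-in total, 12 + 42 = 54 matches the planned sample; 6 + 42 = 48 does not.

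**Cumulative threshold at 16.** 3/16 = 18.75%, continue; 4/16 = 25%, stop. The arm is certain to stop at 16 once a fourth patient has had a SigAE.

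**Which rule acts first.** With L lead-in patients having a SigAE, certainty needs 4 − L more among the next ten; the 3-in-10 rule needs 3.

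| L | More needed for certainty | Most patients enrolled after certainty |
|---|---|---|
| 0 | 4 | 0 (3-in-10 acts first) |
| 1 | 3 | 0 (both act together) |
| 2 | 2 | 8 |
| 3 | 1 | 9 |
| 4 to 6 | 0 | 10 |

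This step needs no assumed rate. It takes one SigAE per patient, all 16 treated, and the 3-in-10 rule acting at the third event.

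**How often.** An arm over-enrols if certainty arrives at or before the ninth of the ten, so that at least one more patient follows. With X ~ Binomial(9, p):

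P(affected) = P(L = 2)·P(X ≥ 2) + P(L = 3)·P(X ≥ 1) + P(L ≥ 4)

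At p = 0.20:

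- P(L = 2) = 15 × 0.2² × 0.8⁴ = 0.2458
- P(L = 3) = 20 × 0.2³ × 0.8³ = 0.0819
- P(L ≥ 4) = 0.0154 + 0.0015 + 0.0001 = 0.0170
- P(X ≥ 2) = 1 − 0.8⁹ − 9 × 0.2 × 0.8⁸ = 0.564
- P(X ≥ 1) = 1 − 0.8⁹ = 0.866
- P(affected) = 0.1386 + 0.0709 + 0.0170 = 0.226

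Full enumeration (seven lead-in counts, 1,024 outcome patterns for patients 7 to 16) gives the same value. The remaining results are:

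| Assumed risk per patient | 10% | 20% | 30% | 40% |
|---|---|---|---|---|
| Arms with L ≥ 2 | 11% | 34% | 58% | 77% |
| Affected, immediate reporting, no halt at lead-in | 3% | 23% | 51% | 74% |
| Affected, lead-in review halts at 3 or more of 6 | 2% | 14% | 26% | 29% |
| Affected, SigAEs after lead-in known three enrolments late | 2% | 16% | 42% | 68% |
| Affected, halt and late reporting together | 1% | 8% | 19% | 24% |
| Affected, given exactly L = 2, immediate reporting | 23% | 56% | 80% | 93% |
| Arm stops by patient 16 (no halt at lead-in) | 10% | 45% | 79% | 94% |

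Extra patients in an affected arm average about 4 with immediate reporting and no lead-in halt, and 2 to 3 with the 3-of-6 halt. At p = 5%, 0.3% of arms are affected.

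**The case against.** The lead-in is a real decision point. Section 3.2 has randomization resuming only once the dose is established for each arm, and 9.1.1 allows an arm to be dropped. The gap needs an arm with at least 2 of 6 (33%), already above the plan's 20%, to pass that review. The figures without a halt assume that the review stops nobody, even at 6 of 6; of the affected arms, 49% at 30% risk and 61% at 40% risk have three or more lead-in SigAEs. Monthly Site Committee discussion (7.6.2), six-weekly DSMC meetings (7.6.3.1) and the adverse-event-rate report and investigator stop in 7.6.4 also make a long overrun less likely. This stands as a reason to weigh the halted-arm figures. It does not close the gap, because none of these passages gives a SigAE count that binds.

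Low risks are also plausible. Section 7.3.2 excludes steroid-controlled irAEs (apart from ocular events needing systemic steroids) and endocrinopathies controlled with hormone replacement. Table 3 shows 7.0% grade 3-4 irAEs at 3 mg/kg. Table 1 shows 21.3 + 4.4 + 0.7 = 26.4% drug-related grade 3 to 5 events over all doses, irAEs included. These data come from other settings and do not fix the rate, but they make 30% and 40% look like stress cases. Averaged over all arms, the excess is 0.01, 0.13 and 0.94 patients per arm at 5%, 10% and 20%. This stands too.

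Finally, the absence of a gap at L = 0 or 1 is conditional. If the 3-in-10 rule is checked only after all ten, those arms can over-enrol as well. If one of the 16 is randomized but not treated, 3/15 = 20% stops the arm and the gap reaches L = 1. Both points widen the problem.

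**Conclusion.** The concern holds. The gap follows from the two rules by arithmetic alone: with two or more lead-in SigAEs in an arm, the stop at 16 can be certain while no written rule halts accrual. Its frequency depends on a risk that the documents do not give. It is negligible at 5%. At 20% it ranges from 8% of arms (lead-in halt at 3 of 6 and late reporting) to 23% (neither). At 10% and 20%, 89% and 66% of arms have 0 or 1 lead-in SigAEs and cannot show it under the stated reading. The flaw does not change which arms stop by patient 16, only how many patients are enrolled first. The missing DLT definition, the event-versus-patient count and the 6-versus-12 lead-in size are plain inconsistencies that need no assumed rate. The lead-in size matters to the rule: with 3 per arm, the cumulative look would come at 13 patients, where 3/13 = 23% stops. This should be corrected, but it does not undermine the design.

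**What to change.** Apply the plan's own 20% rule as soon as its result is certain: count the lead-in patients from the start, and stop accrual to an arm once a fourth of its first 16 patients has had a SigAE. Keep the 3-in-10 trigger. State that both stages count patients with a SigAE, not events. Correct 9.1.1 to 12 lead-in patients (6 per arm), and reconcile its DLT reference with 3.1 and with the SigAE definition in 7.3.2.

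The cost is amendment wording and a running SigAE count per arm. Sample size does not change. Every arm stopped earlier would have stopped at 16 in any case, so the stopping probabilities in the last row of the table stay the same.

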9.3 Methods for Analysis

9.3.1 Primary Endpoints

9.3.1.1 *Safety Lead-in: Assess the safety of combining ipilimumab with SipT.*

Toxicities will be reported for each study arm at each dose of ipilimumab administered with descriptive statistics (e.g. proportions) by tabulating the frequency of the maximum grade occurring for each patient for each type using NCI CTC v. 4.0 criteria. As described above the type and grade of all such IraEs will be tabulated by treatment arm. Toxicity results will be presented indicating occurrences during the first 20 weeks of protocol therapy and those occurring later.

9.3.1.2 *Phase 2: Determine whether the timing of ipilimumab administration impacts PAP and PA2024 specific immune responses by SipT*

The primary immune study hypothesis to assess the frequency of observing an immune response to PAP and/or PA2024 by week 20, when the induction ipilimumab therapy is completed, for each of the two ipilimumab schedules will be tested using the single sample binomial exact test. The IgM and IgG antibody responses to PAP and PA2024 will be assessed with an ELISA assay at baseline and week 20 after the start of sipT treatment (day 113 of study treatment). A positive response will be defined as a titer > 1:400. The primary hypothesis will be tested by comparing the proportion of patients achieving an IgG immune response to PAP or PA2024 to the null hypothesis of 15% (based off an observed anti-PAP IgG response rate of 17.7% seen at a similar time interval in patients treated with sipuleucel-T in the three phase 3 clinical trials⁴⁶. using a single sample exact test for binary variables as defined above in the sample size justification. The same single sample test will be performed for IgM antibodies. The positive immune proportion for both IgG and IgM antibodies to PAP and to PA2024 with 95% confidence intervals will be used to summarize the results for each study arm. No adjustment for multiple comparisons will be made.

Exploratory analyses investigating the change in antibody response from baseline to week 20 when response is considered as a binary variable (positive or negative) will be investigated using the Mantel-Haenszel chi square statistic stratified by treatment arm. When the ELISA results are treated as continuous variables the change in each immune response will be analyzed using analysis of variance (ANOVA) methods.

9.3.2 Secondary Endpoints

9.3.2.1 PSA Decline

Descriptive statistics will be used to characterize the disease and treatment factors for patients accrued to each study arm. The two treatment arms will be compared for comparability of baseline disease features and immune parameters using a chi square test for categorical variables, a t test for normally distributed continuous variables and the nonparametric Mann-Whitney test when the normality assumption cannot be assumed.

Descriptive statistics will be calculated to characterize the proportion of patients achieving a PSA decline of at least >30% and >50% and presented along with the 95% confidence intervals for each study arm. The maximum overall change in PSA will be summarized by waterfall plots for each study arm. Similarly, the proportion of patients achieving an objective response will also be determined. Descriptive statistics will be presented for each study arm to summarize response according to important disease features such as LDH (abnormal vs. normal) and prior treatment (radiation therapy, RP, systemic steroid usage > 3 months). Descriptive statistics will be used to summarize time to PSA progression. The Kaplan-Meier product limit will be used to estimate the probability of time to PSA progression with durations measured from the start of protocol therapy. For each study arm the median time to progression with 95% confidence intervals will be presented to summarize clinical efficacy.

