- To assess the impact of the timing of ipilimumab treatment on the induction of IgG antibodies by SipT, the proportion of patients on each study arm who achieve an immune response to PAP and/or PA2024 at study week 20 will be determined. A positive immune response is defined as a titer > 1:400.

Secondary

- To assess the safety of immediate sequential vs. delayed sequential ipilimumab following SipT the maximum grade of each toxicity and adverse event according to the NCI CTCAE v4 as well as immune related adverse events (see section 5.4.5) will be tabulated for each study arm.
- Clinical activity will be assessed separately for each study arm by:
 - the proportion of patients achieving a PSA decline of at least 30% and at least 50% below baseline using PSAWG2 criteria
 - the proportion of patients achieving a radiographic clinical response according to the immune-related response criteria
 - median time to progression with the duration of time to progression for each patient measured from the start of protocol therapy until progression after 4 cycles of protocol therapy
- Modulation of Effector and Regulatory T Cells:
 - Measures of T cell immune activation will be compared between the two study arms. Summary descriptive statistics including means, mean change from baseline and proportions will be presented for each study arm. Measurements of a T cell response to PAP and PA2024 using IFNg ELISPOT will be obtained over time. A positive response

is defined at ≥ 10 spots/300,000 and will be assessed through week 32. The change from baseline in activated CD4 and CD8 T cells as well as for FoxP3+ CD4+ regulatory T cells will be evaluated through week 20.

PROTOCOL SIGNATURE PAGE

Protocol No.: 12557

Version Date: November 17, 2016

1. I agree to follow this protocol version as approved by the UCSF Protocol Review Committee (PRC), Committee on Human Research (CHR), and Data Safety Monitoring Committee (DSMC).
2. I will conduct the study in accordance with applicable CHR requirements, Federal regulations, and state and local laws to maintain the protection of the rights and welfare of study participants.
3. I certify that I, and the study staff, have received the requisite training to conduct this research protocol.

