- g. Bone scans are at baseline, day 85 (+/- 7 days), and every 12 weeks (+/- 7 days) until PD is reached; can be more often if clinically indicated.
- h. Every Clinic visit will include clinical monitoring for clinical autoimmunity as outlined in Appendix 2.
- i. Q3month follow-up visits should continue until PD or 2 years, whichever comes first.
- j. Blood for Immune Monitoring does not need to be repeated on Day 1 if drawn within 15 days of Day 1.

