7.1.3.1 Definition of PSA Decline

All patients, with or without measurable disease, will be evaluated for PSA decline.

Patients with disease that is not measurable will be eligible for this study and will be assessed for response based on changes in PSA and serial bone scans. The baseline serum PSA must be at least 2 ng/mL.

30% PSA Decline: PSA decline of at least 30% from baseline confirmed by a second measurement at least 4 weeks later. The reference for these declines should be a PSA measured within 2 weeks prior to starting therapy.

50% PSA Decline: PSA decline of at least 50% from baseline confirmed by a second measurement at least 4 weeks later. The reference for these declines should be a PSA measured within 2 weeks prior to starting therapy.

PSA Progression: If at least a 50% PSA decline has been achieved, PSA progression occurs when the PSA has increased to 25% above the nadir and the increase in the absolute-value PSA level is at least 2 ng/mL, or back to baseline, whichever is lower, on at least 2 consecutive measurements at least 1 week apart. For patients without a PSA decline of this magnitude, or without any decline in PSA, progression will be defined by a 25% increase over baseline or nadir PSA (whichever is lower) and an increase in the absolute value PSA level by at least 2 ng/mL, on at least 2 consecutive measurements, after 12 weeks of therapy. For all patients without SigAEs, PSA and/or objective progression will not require the patient to discontinue study treatment until at least three cycles of therapy have been administered.

PSA Decline Duration: The PSA decline duration commences on the date of the first 50% decline in PSA. The response duration ends when the PSA value increases by 50% above the nadir, provided that the increase in the absolute-value PSA level is at least 2 ng/mL or back to baseline, whichever is lower. If a patient does not progress for the duration of the study, his data will be censored at the time of last PSA follow-up.

Progressive Disease: Defined by PSA progression or by objective progression (based on RECIST 1.1 criteria or the appearance of two or more new lesions on bone scan, confirmed 6 or more weeks later) more than three months after the initiation of therapy. Although response in this study is defined as a PSA decline, progressive disease is defined as progression by either PSA or objective progression.

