Time to PSA Progression: The start of the time to PSA progression is the day treatment is initiated. The end date is the time of PSA progression as defined above. If a patient does not progress for the duration of the study, his data will be censored at the time of last PSA follow-up.

7.1.3.2 *Definition of Measurable and Non-Measurable Lesions*

Measurable Disease/Target Lesions

All measurable lesions (lesions that can be accurately measured in at least one dimension, longest diameter to be recorded, as ≥ 10 mm with spiral CT) up to a maximum of 5 lesions per organ and 10 lesions total, representative of all involved organs, should be identified as target lesions and recorded and measured at baseline. Target lesions should be selected on the basis of their size (lesions with the longest diameter) and the suitability for accurate repeated measurements (either by imaging techniques or clinically). The sum of the products of the two largest perpendicular diameters (SPD) of all index lesions (5 lesions per organ, up to 10 visceral lesions) is calculated. At each subsequent tumor assessment, the SPD of the index lesions and of new, measurable lesions ($\geq 5 \times 5$ mm; up to 5 new lesions per organ and 10 visceral lesions) are added together to provide the total tumor burden:

$$\text{Tumor Burden} = \text{SPD}_{\text{index lesions}} + \text{SPD}_{\text{new, measurable lesions}}.$$

The overall response according to the irRC is derived from time-point response assessments (based on tumor burden) as follows:

- Complete Response (CR): complete disappearance of all lesions (whether measurable or not, and no new lesions)
 - confirmation by a repeat, consecutive assessment no less than 4 wks from the date first documented
- Partial Response (PR), decrease in tumor burden $\geq 50\%$ relative to baseline
 - confirmed by a consecutive assessment at least 4 wks after first documentation
- Stable Disease (SD), not meeting criteria for CR or PR, in absence of PD
- Progressive Disease (PD), increase in tumor burden $\geq 25\%$ relative to nadir (minimum recorded tumor burden)
 - confirmation by a repeat, consecutive assessment no less than 4 wks from the date first documented

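### Time to progression is defined as PSA or objective progression, but the only Kaplan-Meier method given is for PSA progression; a median taken from that curve would equal or exceed that of the defined endpoint

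*Combined protocol and SAP*

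**What the plan says.** The secondary endpoints in the synopsis include, for each arm, the "median time to progression with the duration of time to progression for each patient measured from the start of protocol therapy until progression", with the added condition that this progression falls after four cycles. The wording does not limit progression to PSA. Section 1.1 also names time to progression, with PSA decline, as a measure of clinical efficacy.

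Sections 7.1.3 and 7.1.3.1 define the event: "progressive disease is defined as progression by either PSA or objective progression". Section 7.1.3.1 counts it only when it occurs "more than three months after the initiation of therapy". The same section defines time to PSA progression as a separate variable with its own censoring rule: "If a patient does not progress for the duration of the study, his data will be censored at the time of last PSA follow-up".

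The analysis is in section 9.3.2.1, headed PSA Decline. It reads "The Kaplan-Meier product limit will be used to estimate the probability of time to PSA progression with durations measured from the start of protocol therapy", and then "For each study arm the median time to progression with 95% confidence intervals will be presented to summarize clinical efficacy". Section 9.3.2.2 adds only a radiographic response proportion with a confidence interval. No other part of section 9 describes a time-to-event analysis of progression.

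**The concern.** The endpoint and its definition are composite, while the estimator is attached to one component. The sentence promising the median follows directly on the PSA Kaplan-Meier sentence and names no other event, estimator or censoring rule. An analyst following the text would most naturally read the median from the PSA curve and label it time to progression.

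A man with new lesions on a scan but no PSA progression would then not be counted as a failure, although section 7.1.3.1 says he has progressed. Time to progression is one of the few clinical-activity measures that the trial will report by arm. Two analysts working from the same data could publish different medians, and the PSA-only choice would favour both arms.

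**Working it through.** **The plan's own figures.** The documents give no assumed median, event count or share of scan-first progressions, so there is no figure to reproduce on this point. The primary sample size does not use time to progression. For reference, 27 patients per arm with 15% against 40% and a two-sided 5% level reject at 9 or more responses (upper tail 0.0138, limit 0.025). The exact power is 0.816, which agrees with the stated 81%.

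**Step 1: direction.** Let P be the time to PSA progression, Q the time to objective progression, and C = min(P, Q) the defined endpoint. For every patient C ≤ P, so the median of C cannot exceed the median of P. On the Kaplan-Meier scale, suppose that a scan-first patient leaves the risk set on the date of his scan progression. The PSA curve then has the same risk sets and fewer events, so it cannot lie below the composite curve. Censoring him somewhat earlier, at his last PSA, can disturb this slightly in a small sample but does not change what is being estimated.

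**Step 2: would scan-first patients be censored?** No rule names them. The PSA clock in 7.1.3.1 ends at PSA progression and otherwise at the last PSA. Footnote i of section 6.1 says "Q3month follow-up visits should continue until PD or 2 years, whichever comes first". Section 3.3 limits follow-up to the date of death for patients who stop ipilimumab for clinical progression and switch treatment. For many scan-first patients the PSA record would therefore end near the scan progression. This is an inference from the visit schedule, not a stated rule.

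**Step 3: size under independence.** Inputs:
- L = 3 months before progression counts (7.1.3.1).
- m = 6 months, the composite median (assumed).
- s, the share of progressions seen first on scans (assumed; not in the documents).
- Constant, independent hazards after L for both components.

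The total hazard after L is ln 2/(m − L), and the PSA part is (1 − s) of it. Hence the PSA-only median = L + (m − L)/(1 − s).

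| s | Calculation | PSA-only median (months) |
|---|---|---|
| 0 | 3 + 3/1.0 | 6.0 |
| 10% | 3 + 3/0.9 | 6.33 |
| 20% | 3 + 3/0.8 | 6.75 |
| 30% | 3 + 3/0.7 | 7.29 |
| 40% | 3 + 3/0.6 | 8.0 |

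Over s = 10% to 50%, a composite median of 4 months becomes 4.1 to 5.0, and one of 9 months becomes 9.7 to 15.0.

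**Step 4: correlated times.** PSA and scan times in one patient are likely to be related. A simulation (40,000 patients per scenario, 24-month cap, three-month lead-in) kept the separate PSA and scan hazards of the s = 30%, m = 6 case and varied the correlation on the underlying normal scale.

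| Correlation | Observed scan-first share | Composite median | PSA-only Kaplan-Meier median |
|---|---|---|---|
| 0 | 0.30 | 6.01 | 7.29 |
| 0.5 | 0.23 | 6.54 | 7.77 |
| 0.8 | 0.13 | 6.98 | 7.77 |

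The true median of P is 7.29 in all three rows. Under independence the Kaplan-Meier estimate is correct for P, and the gap is purely a difference between two quantities. Under positive correlation the censoring is informative, and the estimate also exceeds the median of P. The PSA-only median was the longer in every scenario run. The smallest gap was 4.11 against 4.12 months, with 1% of patients progressing first on scans.

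**The case against.** The best defence is that 9.3.2.1 promises two outputs: a PSA Kaplan-Meier curve, and a median time to progression that omits the word PSA. The paragraph also covers objective response, so its heading does not confine it to PSA. Section 7.1.3 plans independent reporting of measurable, non-measurable and PSA findings. This stands to the extent that the text is ambiguous. A reader might infer that the plan definitely analyses PSA progression alone and that the reported median will be too long; the documents do not settle that. But if the second sentence does mean the composite, its estimator and censoring rule are missing, so the text needs changing either way.

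A reader might also infer that all follow-up stops at progression and that scan-first patients are expressly censored. In section 4.3 and footnote i of 6.1, the progression limit attaches to the quarterly visits. The monthly visits in 6.2.1.3 include PSA, section 3.3 allows reinduction after progression, and new bone lesions need confirmation 6 or more weeks later. Some PSA records will run past a first positive scan.

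On size, a constant hazard from day zero gives 6/(1 − s) = 6.7, 7.5, 8.6 and 10.0 months at s = 10% to 40%, an overstatement of 11% to 67%. Those figures ignore the three-month rule in 7.1.3.1 and double the excess. PSA is also taken every cycle during treatment, against 12-weekly scans, which may keep s low. However, much of that sampling falls before progression can count, and PSA later becomes quarterly. The eligibility criteria (4.1) themselves accept radiographic progression without PSA progression.

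Finally, the trial is non-comparative, and time to progression carries no test, benchmark or decision rule. That limits the consequence but does not remove the mismatch.

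**Conclusion.** The point holds in conditional form. Section 9 gives no time-to-event method for the composite that 7.1.3.1 defines, and the only stated estimator measures PSA progression. If the reported median comes from that curve, which is the most direct reading, it estimates a quantity equal to or longer than the defined endpoint.

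The size cannot be fixed from the documents because s is not given. For an assumed composite median of 6 months with the three-month lead-in and independent times, the excess is about 0.3, 0.75, 1.3 or 2.0 months at s = 10%, 20%, 30% or 40%, and zero at s = 0. The effect is confined to a secondary, descriptive summary. It is worth correcting because the direction is known and the remedy is cheap.

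**What to change.** In 9.3.2.1, state that the median time to progression is the Kaplan-Meier median, with 95% confidence interval, of the composite in 7.1.3.1: the first of PSA or objective progression. Keep time to PSA progression as a separate, labelled analysis.

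For each analysis, state how scan-first progression, the start of new therapy and death are handled. Keep the endpoint as time to progression and report deaths before progression separately, for example as a competing event. Counting death as an event would turn it into progression-free survival, which the protocol does not list.

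Before the composite is derived, reconcile the criterion for objective progression. The progressive-disease definition in 7.1.3.1 uses RECIST 1.1, while 7.1.3 and 7.1.3.2 assess lesions by irRC, under which new lesions alone do not make measurable disease progressive.

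PSA, scans and dates of death are already collected, so no new assessments are needed. The cost is revised wording, that reconciliation and a little more analysis work; the reported median may be shorter.
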